21 June 2023

Protocol

Title: Association between use of direct oral anticoagulants (DOACs) and increased risk of interstitial lung disease

Administrative details of the data analysis	
Substance(s)	Edoxaban, Apixaban, Rivaroxaban, Dabigatran
Condition/ADR(s)	Interstitial lung disease
Short title of topic	ILD and DOACs
Study team	[name], [name] and [name]

1. List of abbreviations

MAH	Marketing Authorisation Holder
EMA	European Medicines Agency
PRAC	Pharmacovigilance Risk Assessment Committee

2. Milestones

Milestone	Planned date
Draft analysis plan prepared	24/03/2023
Revised analysis plan following review	21/06/2023
Final analysis report	TBD

3. Rationale and background

Interstitial lung disease (ILD) describes a heterogenous group of respiratory disorders affecting the interstitium of the lungs. [1,2] ILD may occur when an injury to the lungs triggers an abnormal healing response. The repair process is disrupted, and the tissue around the alveoli becomes scarred and thickened. Prolonged ILD may result in pulmonary fibrosis, but this is not always the case. [1,2]

Cases of interstitial lung disease (ILD) have been recently described, especially in Asian subjects, in people using direct oral anticoagulants (DOACs) [3-5]. In addition, a recently published observational study suggests an increased risk of ILD in patients treated with factor Xa inhibitors (edoxaban, apixaban, rivaroxaban) as compared to warfarin users among subjects with non-valvular atrial fibrillation in Taiwan [6, 7], which triggered a new potential safety signal. A thorough review of this issue within the ongoing and upcoming PSUSA procedures for edoxaban, apixaban and rivaroxaban is expected. In this context, a real-world data (RWD) analysis has been requested to better inform the PRAC on the relationship between increased risk of ILD and use of DOACs in the European population.

4. Research question and objectives

Is the use of factor Xa (FXa) inhibitors (edoxaban, apixaban and rivaroxaban) or direct thrombin inhibitor (dabigatran) associated with an increased risk of interstitial lung disease (ILD) when compared with patients treated with vitamin K antagonists (VKA), among patients with Atrial Fibrillation (AF), Deep Vein Thrombosis (DVT) and Pulmonary Embolism (PE)?

5. Research methods

5.1. Study design

Propensity score matched comparative cohort studies with two-stage meta-analysis.

5.2. Data sources

The following databases will be used: IQVIA™ Medical Research Data (IMRD) UK, IQVIA™ Disease Analyser Germany, and THIN® Spain and Italy. These databases have been mapped to the OMOP (Observational Medical Outcomes Partnership) CDM (Common Data Model) version 5.3. Brief descriptions of these databases are provided in **Annex 1**.

5.3. Setting and study population

The included study population will consist of adult new users of the anticoagulants of interest (see section on Exposures), as recorded for patients visiting general practices (UK, Germany, Spain, and Italy). Patients will require to have been observed at least once at minimum one year (365 days) prior to entering the cohort. In the UK database, this will be defined as a minimum of 365 days between registration with the practice and the index date. For the other databases, this will be defined as a record of health care system use recorded in the databases at least 365 days prior to the index date.

The population will be stratified by indication for anticoagulation, namely for the management of atrial fibrillation (AF) or for the management of venous thromboembolism (VTE, namely deep vein thrombosis or pulmonary embolism). Indications will be identified by the presence of diagnosis codes within the individual's electronic health record in the year up to the index date. Patients initiating anticoagulation with no diagnostic code for AF or VTE will not be included in the analysis. For patients with multiple indications, the most recent indication (before index date) will be used. Patients with a history of cardiac mechanical valve or mitral stenosis prior to cohort entry will be excluded, as they have an indication for warfarin, not DOACs.

Individuals with a diagnosis of ILD prior to cohort entry (anytime in the patient's prior history) will be excluded from the cohort.

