5.4. Study period

The study observation period to identify new users will be from 1st of January 2010, to 31st of December 2019 (i.e., the period before COVID-19 cases emerged).

Cohort entry will be the date of anticoagulant initiation (**index date**). New anticoagulant use will be defined as no prescription for any anticoagulant of interest in the 365 days prior to cohort entry.

Cohort exit will be the earliest of ILD, death (for databases where death is captured), end of individual observability (deregistration or end of practices contributing data where these data are captured), treatment switching (for the on-treatment analysis) or end of the study period (31st December 2019). For the analysis of any DOAC vs VKA, switching to a different DOAC will not be considered a switch of exposure.

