5.6.2. Main statistical methods

Propensity score matching will be performed using a 1:1 matching of warfarin users to DOAC users using a caliper width of 0.2 of the standard deviation of the logit of the propensity score. [11] We will include the baseline risk factors and calendar year as predictor variables in the propensity score. Matching will occur by indication (AF and VTE). Absolute standardised mean differences (SMD) for each variable will be calculated before and after propensity score matching, with SMD of less than 0.1 representing successful matching. We will visually check the distributions of the propensity scores across treatment arms, within strata (indication, database). If the sample size appears insufficient after matching, we will use Inverse Probability Treatment Weighting (IPTW) instead of matching.

In the propensity-matched cohort, the incidence of each study outcome will be estimated between target (DOAC) and comparator (warfarin) groups. Cox models will be used to calculate hazard ratios for the instantaneous risk of the ILD outcome. Where death is available in the data source, competing

mortality risk will be accounted for by estimating cause-specific hazard functions. We will apply two analytical approaches: an **on-treatment analysis** (OT) and an **intention to treat analysis** (ITT as per the study by Chan et al.).

Summary of key analysis factors:

- 4 Countries
- 4 DOACs + 1x all DOACS = 5 (warfarin is comparator)
- 2 indications

This brings the number of analyses to $4 * 5 * 2 = 40$ (this number will vary depending on the analytical approach and principal findings).

5.6.3. **Meta-analysis**

Hazard ratios will be reported for each database, exposure and indication separately. Log hazard ratios will also be meta-analysed across databases using a random-effects model using REML (Restricted Maximum Likelihood). 95% Confidence intervals will be provided using the HKSJ method. [12, 13] 95% approximate prediction intervals will be provided. [14] I^2 will be estimated to describe the percentage of the variability in effect estimates that is due to heterogeneity rather than sampling error.

5.6.4. **Missing data**

The analysis will be conducted on the assumption that an individual has a condition or prescription exposure if it is recorded in their electronic health record. No multiple imputation methods will be performed. Therefore, patients with missing records for an indication will be excluded from the analyses.

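### Outside the UK, one record of any age satisfies the prior-observation rule, so the 365-day washout can cover an unobserved year and continuing anticoagulant users can enter as new users

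*Protocol*

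**What the plan says.** Protocol section 5.3 states a general requirement: "Patients will require to have been observed at least once at minimum one year (365 days) prior to entering the cohort". It then defines it in two ways. In the UK it means "a minimum of 365 days between registration with the practice and the index date", which is a registered interval. In Germany, Spain and Italy it means "a record of health care system use recorded in the databases at least 365 days prior to the index date", which is a single dated event.

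Section 5.4 sets the washout: "New anticoagulant use will be defined as no prescription for any anticoagulant of interest in the 365 days prior to cohort entry".

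Section 5.6.4 (Missing data) assumes that "an individual has a condition or prescription exposure if it is recorded in their electronic health record", and rules out multiple imputation.

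Two other rules bear on the point, both in section 5.3. The ILD exclusion is not limited to one year: "Individuals with a diagnosis of ILD prior to cohort entry (anytime in the patient's prior history) will be excluded from the cohort". For the indication, "Indications will be identified by the presence of diagnosis codes within the individual's electronic health record in the year up to the index date".

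**The concern.** A new-user design needs a washout in which a prescription would have been seen had there been one. The UK rule gives at least a registered year. The non-UK rule sets no upper limit on the age of the qualifying record and asks for nothing between that record and index. If the patient was treated elsewhere in the meantime, the washout finds no prescription because there was no observation.

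Such a patient is a continuing user with a false time zero: the early period of exposure has been missed, and the patient has already remained on treatment for some time. In a safety study of a drug reaction, that undermines the reason for restricting to initiators. Because the rule differs between the UK and the other three databases, any resulting bias could also appear as heterogeneity in the meta-analysis of section 5.6.3.

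**Working it through.** The protocol states no figure on this point, so there is nothing to reproduce. The main check is one of logic.

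**Step 1: apply the rules as written.** Non-UK prior observation: any record at day -365 or earlier. Washout: no recorded anticoagulant prescription from day -365 to day -1.

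| Test patient (index = day 0) | Prior observation | Washout |
|---|---|---|
| One record at day -366, then index | passes | passes |
| One record at day -3000, then index | passes | passes |
| One record at day -900, anticoagulant prescribed elsewhere and unrecorded | passes | passes |
| Recorded anticoagulant at day -400, then no records until index | passes | passes |

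All four enter as new users. The third is a continuing user. The fourth may be one, if prescribing continued elsewhere.

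**Step 2: does the indication code close the gap?** It must fall in the year up to index, but one code at the index visit or a few days before is enough. It shows contact on that day, not a year of observation.

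**Step 3: which other rules depend on the washout year?** The ILD exclusion searches all recorded history, and section 5.5 applies a composite of any ILD-related code. Section 5.5 sets no 365-day window for covariates: most comorbidities are listed as a history, and smoking uses the most recent status before index. These fail only for conditions never recorded in the database.

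**Step 4: what does Annex 1 show?** THIN Spain: 1,050,000 of 3,000,000 individuals were active in the previous year (35%). THIN Italy: 500,000 of 900,000 are actively followed (56%). The totals include patients who have died or left, so these are not empty-year rates among initiators. They show only that an old record is weak evidence of current observation.

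**Step 5: how common could an empty year be?** Assumption, not in the documents: visits occur at random at rate v per year, so P(no record in 365 days) = exp(-v). This gives 61% at v = 0.5, 37% at 1, 14% at 2, 1.8% at 4 and 0.2% at 6.

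**Step 6: illustration for the secondary ILD route only.** Observed ratio = (HR × I + c1)/(I + c0), where I is the comparator's risk of incident ILD and c1 (DOAC) and c0 (VKA) are the shares with unrecorded earlier ILD that is coded during follow-up. All inputs are assumed.

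- I = 0.3% (1 per 1,000 person-years over 3 years), unseen ILD in 0.5% of empty-year patients, all coded later. Empty years in 10% of VKA and 5% of DOAC patients: a true HR of 1.0 gives (3.0 + 0.25)/(3.0 + 0.5) = 0.93, and 1.5 gives 4.75/3.5 = 1.36.
- Same, with empty years in 1.8% and 0.9%: 3.045/3.09 = 0.985, and 4.545/3.09 = 1.47.
- I from 0.2% to 0.5%, c from 0.05% to 0.10%. Equal contamination: a true HR of 1.5 is seen as 1.33 to 1.45. Contamination twice as high in either arm: a true HR of 1.0 is seen as 0.83 to 1.20.

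The result runs from negligible to material, and its direction depends on which arm is more contaminated. The washout route, which is the main point, cannot be quantified from the protocol.

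**The case against.** The strongest case on the other side has four parts.

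- **A reader might infer that patients with known ILD enter as ILD-free, and that baseline covariates are read from an empty year.** The text does not support this. Only the washout is confined to 365 days (Step 3). This part of the objection stands, and the point is limited accordingly.
- **A reader might infer that the VKA arm is more contaminated because VKA is the older treatment, so the HR is pulled down.** That is an inference. The protocol gives no data on it, and depletion of susceptible patients among continuing VKA users would act in the opposite direction. Matching includes calendar year, and patients with sparse records will tend to match one another, which may remove part of any imbalance. No direction can be claimed.
- **Anticoagulated patients are seen often, so empty years may be rare.** This is plausible: at four visits a year the Step 5 illustration gives 1.8%. It bears on size, not on whether the rule is sound, and the protocol plans no count that would settle it.
- **The gap is disclosed.** Section 5.8 concedes that exposures, outcomes or covariates may go unrecorded, and section 5.4 uses deregistration only where it is captured. Neither mentions the look-back rule. The only sensitivity analysis in section 5.6.6 concerns calendar time.

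The UK rule is not perfect either, since registration does not reveal prescriptions issued outside the practice. It does secure a registered year, which the other rule does not.

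**Conclusion.** The point holds for the new-user definition. Read together, sections 5.3, 5.4 and 5.6.4 let an unobserved year count as a clean washout in Germany, Spain and Italy, and neither the indication code nor the stated limitations prevent it. This follows from the wording alone and needs no assumption.

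The consequence is less certain. The number of patients affected and the net direction of bias cannot be determined from the protocol. The ratios in the working rest wholly on assumed inputs and concern the weaker route, through ILD never recorded in the database. They show a possible range and are not an estimate. The rule should be changed before the cohorts are built, because the change is cheap and the failure count would show whether the problem matters.

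**What to change.** In section 5.3, for Germany, Spain and Italy, keep the record at least 365 days before index and add evidence of observation within the washout year that is separate from the index episode. One example is at least one recorded contact between day -365 and day -31, not counting the qualifying AF or VTE code or the index visit. The exclusions matter: if any contact up to day -1 counted, an AF code entered a week before index would satisfy the rule and little would change. All four test patients in the working would fail the added condition.

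Report by arm and database how many initiators fail it, and give results under the current rule as a sensitivity analysis in section 5.6.6.

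The cost is a sentence or two in section 5.3, one filter in the cohort code and one extra set of results. Some low-contact patients outside the UK are lost. One contact does not prove continuous observation, so this is a minimum standard and does not make the databases equivalent to the UK.

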5.4. Study period

The study observation period to identify new users will be from 1st of January 2010, to 31st of December 2019 (i.e., the period before COVID-19 cases emerged).

Cohort entry will be the date of anticoagulant initiation (**index date**). New anticoagulant use will be defined as no prescription for any anticoagulant of interest in the 365 days prior to cohort entry.

Cohort exit will be the earliest of ILD, death (for databases where death is captured), end of individual observability (deregistration or end of practices contributing data where these data are captured), treatment switching (for the on-treatment analysis) or end of the study period (31st December 2019). For the analysis of any DOAC vs VKA, switching to a different DOAC will not be considered a switch of exposure.

5.5. Variables

Outcome:

The outcome of interest will consist of an incident diagnosis of ILD. ILD consists of a heterogeneous group of conditions. The ILD phenotype is therefore a composite of different codes representing ILD in general, or as specific conditions that are classed as an ILD. Exclusion of patients with pre-existing ILD will be evaluated using a composite phenotype consisting of any ILD related code. For the outcome in the analysis, a narrower definition of ILD will be used, namely pulmonary fibrosis, pneumonitis, ILD specific codes, and drug induced ILD (please see Appendix for exemplar codes lists). As codes for drug induced ILD are infrequently used, inclusion of this as a specific subgroup may provide limited information. We followed the "narrow" scope list of terms (i.e., very specific preferred terms) documented in the Introductory Guide for Standardised MedDRA Queries (SMQs) Version 25.0 [8]. We mapped these SMQ codes to SNOMED codes and used their OMOP concept IDs, and subsequently removed any codes that indicate another well-defined cause of ILD. Detailed list of codes included are shown in **Annex 2**.

Exposure:

Exposures of interest will consist of VKAs (comparator, consisting of either warfarin, acenocoumarol, phenindione, or phenprocoumon), and DOACs (target, consisting of apixaban, dabigatran, edoxaban and rivaroxaban). Exposures will be identified through prescriptions recorded in the electronic health record. Target exposures will be evaluated by class (any DOAC (direct oral anticoagulants)) and as individual drug substances.

For the on-treatment analysis, patients will be considered continuously exposed from cohort entry (index date) up to 30 days after the date of the last anticoagulant prescription in the patients record. In order to account for different treatment episodes over time, gaps of >90 days between anticoagulant prescriptions will be considered as different treatment episodes and continuous exposure will be censored 30 days after the last prescription before the gap. Detailed list of codes and terms included to identify exposure to DOACs are shown in **Annex 2**.

Other variables:

Baseline risk factors for ILD will be measured including: age, sex, history of pneumonia, chronic obstructive pulmonary disease, chronic kidney disease, hepatitis C, history of tuberculosis sarcoidosis, history of autoimmune diseases, history of connective tissue disorders, history of sarcoidosis, history of cancer, exposure to medications (nitrofurantoin, sulfonamides, amiodarone, methotrexate, cyclophosphamide, dronedarone, SSRIs/SNRI antidepressants, anticonvulsants, antiplatelets, statins, angiotensin converting enzyme inhibitors (ACEI), angiotensin-II receptor blockers (ARB), thiazide diuretics and systemic fluoroquinolone antibiotics [Detailed list is shown in Annex 2]), smoking status. [9, 10] Smoking status may be missing. We will include current smoking status as a binary variable. An individual will be classed as a current smoker (1) or non-current smoker (0, i.e., other smoking status or the absence of a smoking status) based on the most recent smoking status prior to their index date. Risk factors that will not be reliably identifiable include environment and occupational exposures, family history, and biologics, and will not be considered in the analysis. Information on prior radiotherapy and chemotherapy may not be available for some patients but will be included in the analysis when available.

Additionally, the incidence of ILD has changed substantially over time as well as the prescription patterns of the exposures. We will therefore also account for calendar year in the propensity score analysis.

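### The on-treatment episode rule uses prescription dates only (gap over 90 days, 30-day tail), so an uninterrupted user whose renewals are more than 90 days apart is censored while still supplied

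*Protocol*

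**What the plan says.** Section 5.5 (Exposure) takes exposure from prescription records: "Exposures will be identified through prescriptions recorded in the electronic health record". For the on-treatment analysis, exposure runs from the index date "up to 30 days after the date of the last anticoagulant prescription in the patients record". A further clause handles interruptions: "gaps of >90 days between anticoagulant prescriptions will be considered as different treatment episodes and continuous exposure will be censored 30 days after". Those 30 days are counted from the prescription that precedes the gap.

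The rule covers every substance in the comparison: "VKAs (comparator, consisting of either warfarin, acenocoumarol, phenindione, or phenprocoumon), and DOACs (target, consisting of apixaban, dabigatran, edoxaban and rivaroxaban". Section 5.2 names four databases (UK, Germany, Spain, Italy), and no database-specific version of the rule is given. Quantity supplied, days' supply and daily dose are not mentioned.

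Section 5.4 defines new use as "no prescription for any anticoagulant of interest in the 365 days prior to cohort entry". Section 5.6.2 plans both an on-treatment and an intention-to-treat analysis and does not say which is primary. The only sensitivity analysis in section 5.6.6 concerns calendar-time stratified matching. Neither the 90 days nor the 30 days is varied anywhere.

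**The concern.** How long a prescription lasts depends on the quantity supplied and the daily use. A rule that sees only dates cannot tell a patient who stopped from one who is still working through a long supply. If the supply lasts more than 90 days, an on-time renewal counts as a gap. The patient is then censored 30 days after the previous prescription although treatment never stopped. The later prescriptions form a new episode, but that episode cannot enter the cohort because there were no 365 anticoagulant-free days before it. The remaining treated time is lost.

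The study is meant to inform a regulator on a safety signal. Section 3 describes ILD as scarring that follows a disrupted repair process, so an effect that appears only after some months is plausible. An on-treatment analysis that keeps little time beyond the first weeks in one arm would have little power to see it. Results are also split by database, drug and indication (section 5.6.2) with no sample size stipulated (section 5.6.5), so lost events matter.

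**Working it through.** The protocol states no follow-up length, renewal interval or event count, so there is no figure of its own to reproduce. The check applies the section 5.5 rule to patients who are in truth treated without interruption.

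**Inputs from the protocol:** gap threshold 90 days; tail 30 days; re-entry only after 365 days without a prescription.

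**Assumptions, not in the protocol:** 730 days of true continuous use; mean renewal intervals from 28 to 200 days; interval variability of none, SD 10 days, or a lognormal distribution with coefficient of variation (CV) 20%.

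**Step 1. Renewals exactly on time.** Exposure ends at the last prescription before the first gap over 90 days, plus 30 days, capped at 730.
- 28-, 30-, 56-, 60- or 90-day intervals: 730 days kept.
- 84-day intervals: last prescription at 8 × 84 = 672, so 672 + 30 = 702 days kept.
- 91 days or more: the first interval is already a gap, so 0 + 30 = 30 days kept, or 30/730 = 4.1%.

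Retained time therefore falls from 730 to 30 days between a 90-day and a 91-day interval.

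**Step 2. Variable intervals, CV 20%.** For a lognormal interval with mean m, σ = √ln(1 + 0.20²) = 0.198 and μ = ln m − σ²/2. Let p be the probability that one interval exceeds 90 days. The expected number of intervals completed before a gap is (1 − p)/p. Ignoring the 730-day cap, which hardly matters at these intervals:

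mean days kept = 30 + [(1 − p)/p] × E(interval | interval ≤ 90)

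- m = 98: p = 0.63; 0.588 × 79.0 + 30 = 76 days.
- m = 100: p = 0.67; 0.498 × 79.4 + 30 = 70 days.

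Here p is also the share censored at exactly day 30 of follow-up: 63% and 67%. As a fraction of 730 days, 70 to 76 days is about 10%.

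Simulation with the cap (8,000 users per setting) agrees and extends the range:

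| Mean interval (days) | Mean days kept of 730 |
|---|---|
| 30 | 730 |
| 50 | 719 |
| 60 | 659 |
| 75 | 339 |
| 84 | 180 |
| 90 | 120 |
| 98 | 76 |
| 100 | 70 |
| 120 | 38 |
| 200 | 30 |

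**Step 3. Less variability, SD 10 days.**

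| Mean interval (days) | Mean days kept of 730 | Share cut at day 30 |
|---|---|---|
| 28 | 729 | 0% |
| 56 | 722 | 0% |
| 84 | 235 | 27% |
| 90 | 119 | 48% |
| 98 | 55 | 78% |
| 100 | 48 | 83% |
| 112 | 31 | 99% |

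The loss is small up to mean intervals of about 60 days under either assumption, and heavy from about 75 to 84 days upward.

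**Step 4. Effect on the hazard ratio if arms differ.** This simulation used 1,500 patients per arm, 12 replicates and a deliberately raised hazard. Both arms renewing every 28 days was compared with DOAC 28 days and VKA 100 days (SD 10 in each).

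| True effect | HR, both arms 28 d | HR, 28 d vs 100 d | Events, both 28 d | Events, 28 d vs 100 d |
|---|---|---|---|---|
| HR 1.0 throughout | 0.98 | 1.02 | 1356 | 736 |
| HR 1.5 throughout | 1.47 | 1.53 | 1560 | 946 |
| HR 1 to day 180, then 2 | 1.67 | 1.07 | 1634 | 1035 |

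Under proportional hazards the estimate barely moves, but events fall by 1 − 736/1356 = 46% and 1 − 946/1560 = 39%. With a delayed effect the estimate falls from 1.67 to 1.07, because the late period is seen almost only in one arm.

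**The case against.** The strongest reply is that the harm depends on figures that the protocol does not contain. It gives no pack size, dosing frequency or renewal interval for any drug or country, and the written rule is identical everywhere. A reader might infer that arms and countries are in fact truncated unequally; the documents do not show that. It follows only if renewal intervals differ, which is a reasonable risk across titrated VKAs, DOACs and four health systems, but no more than a risk. This part of the objection stands.

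Three further limits also stand. First, a reader might infer that all long-supply users are cut at day 30. That holds only when the first interval exceeds 90 days; otherwise the cut comes 30 days after the last prescription before a later gap. Second, a reader might infer that the on-treatment hazard ratio is biased in general. Step 4 shows mainly lost events under proportional hazards, with a shift only when the effect varies with time. A link between renewal length and prognosis could also matter but was not examined. Third, the intention-to-treat analysis does not use this rule and keeps later follow-up.

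It can also be said that the gap clause does not state outright that it counts from date to date. That is true, but the tail is anchored on prescription dates and no end of supply is defined from which a gap could be counted, so date-to-date is the natural reading.

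None of this removes the core point: time kept depends on the renewal interval rather than on whether the patient is treated, and no planned analysis tests that.

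**Conclusion.** The point holds for the on-treatment analysis only. As written, the rule censors uninterrupted users whose renewals are more than 90 days apart while they are still supplied, and the new-user definition prevents their return. The size is conditional. At mean intervals of 98 to 100 days, about 70 to 76 of 730 days are kept with an assumed CV of 20%, 48 to 55 with an SD of 10 days, and 30 with exact renewals. At mean intervals up to 60 days, at least 659 of 730 days are kept under the variability assumed here.

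Unequal follow-up by arm or database, loss of events and a masked delayed effect are possible consequences that the renewal data would confirm or exclude. The documents support neither a claim that truncation is already known to be unequal nor a claim that the study's hazard ratios are biased overall. Because the rule is fixed in the text and no sensitivity analysis varies it, it should be changed or tested before outcomes are examined.

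**What to change.** Before outcomes are examined, tabulate the interval between consecutive prescriptions by substance and database. This shows at once whether any arm or country comes near 90 days.

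In section 5.5, define the end of an on-treatment episode from the estimated end of supply. Use recorded quantity or days' supply where available, and otherwise a substance- and database-specific interval such as the 90th percentile of time between consecutive prescriptions. Use the same type of estimate in both arms of each comparison; recorded supply for DOACs against a percentile for VKAs would itself create an asymmetry. Apply one common permissible gap after the end of supply.

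At minimum, keep the present rule and add to section 5.6.6 two prespecified sensitivity analyses: the supply-based definition, and a longer gap and tail. In either case, report on-treatment follow-up time and events by arm and database.

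The cost is protocol wording and extra programming. The protocol does not confirm that quantity fields exist in all four databases, so the percentile route may be needed in some. Days' supply for titrated VKAs will remain an estimate.

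### On-treatment exposure in days 31 to 90 after a prescription depends on whether another prescription follows, so ILD that ends treatment can be lost from that analysis

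*Protocol*

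**What the plan says.** Protocol section 5.5 (Exposure) sets the on-treatment window. Three of its statements matter here.

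- The window runs from the index date "up to 30 days after the date of the last anticoagulant prescription in the patients record".
- Episodes are split only by long gaps: "gaps of >90 days between anticoagulant prescriptions will be considered as different treatment episodes". By implication, a gap of 90 days or less stays inside the episode and counts as exposed throughout.
- Where a gap does exceed 90 days, the prescriptions on either side of it are to be "considered as different treatment episodes and continuous exposure will be censored 30 days after the last prescription before the gap".

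On the data behind the rule, the section says: "Exposures will be identified through prescriptions recorded in the electronic health record". Neither days' supply nor prescription length enters the window.

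Section 5.4 makes exit the earliest of several events, ILD among them, and lists "treatment switching (for the on-treatment analysis) or end of the study period". Section 5.6.2 plans both an on-treatment and an intention-to-treat (ITT) analysis and names neither as primary. The only sensitivity analysis, in section 5.6.6, concerns matching by calendar time. The limitations in section 5.8 do not mention the exposure window.

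**The concern.** Whether day 45 after a prescription is exposed cannot be known on day 45. It depends on whether a further prescription is written by day 90. If one is, day 45 counts. If none is, exposure is cut back to day 30.

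This matters because the outcome can decide the answer. Suppose ILD is recorded on day 45. If the patient is prescribed an anticoagulant again by day 90, the event counts. If the ILD leads to stopping and nothing follows, the censoring date precedes the event and the event is lost. Censoring is then informative, and it acts on the kind of event the study was set up to detect: ILD that a prescriber may attribute to the drug. The outcome definition in section 5.5 includes drug-induced ILD.

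At the least, events are lost for an uncommon outcome. If refill intervals or stopping after ILD differ between DOAC and VKA users, or between countries, the on-treatment hazard ratio is also distorted.

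**Working it through.** The protocol states no refill interval, stopping probability, diagnostic delay or expected number of events, so it has no figure to reproduce. The inputs are:

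- From section 5.5: a 30-day tail after the last prescription, and a 90-day limit for bridging a gap.
- Assumed: refill interval *g* of 28, 56 or 84 days; probability *p* that no anticoagulant prescription follows the ILD in time; ILD onset uniform over the interval.

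**Step 1. Share of events counted, ILD diagnosed at once.** Let *m* = min(30, *g*)/*g*. An event in the first 30 days always counts; a later one counts only if a prescription follows. The share is *f* = *m* + (1 − *m*)(1 − *p*).

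| *g* (days) | *m* | *p* = 0.3 | *p* = 0.5 | *p* = 1 |
|---|---|---|---|---|
| 28 | 1 | 100% | 100% | 100% |
| 56 | 30/56 = 0.536 | 86% | 77% | 54% |
| 84 | 30/84 = 0.357 | 81% | 68% | 36% |

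For example, at *g* = 84 and *p* = 0.5: 0.357 + 0.643 × 0.5 = 0.679.

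**Step 2. Effect on the hazard ratio.** For a rare event, person-time hardly changes, so the apparent HR is about the true HR × *f*(DOAC)/*f*(VKA). Take a true HR of 1.0, equal *p* in both arms, and refills of 28 days (DOAC) and 84 days (VKA):

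- *p* = 0.1: 1/0.936 = 1.07
- *p* = 0.3: 1/0.807 = 1.24
- *p* = 0.5: 1/0.679 = 1.47

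With the intervals reversed, the HR is 0.81 at *p* = 0.3 and 0.68 at *p* = 0.5. With equal intervals and equal *p* the two shares cancel.

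**Step 3. Delayed diagnosis.** A simulation let the drug stop at ILD onset and the diagnosis follow after an exponential delay with mean 30 days. Background discontinuation was 0.25 per year (all assumed). The share of drug-stopping ILD counted was:

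| *g* (days) | 30-day tail, as written | 90-day tail |
|---|---|---|
| 28 | 39% | 92% |
| 56 | 20% | 86% |
| 84 | 13% | 73% |

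Among patients who continued despite ILD, 98.5%, 96.9% and 95.6% of events were counted under the rule as written.

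The rate ratio, with a true value of 1.5 and the same delay, was:

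| Scenario | 30-day tail | 90-day tail |
|---|---|---|
| Equal intervals, ILD always stops the drug (*g* = 28, 56, 84) | 1.50, 1.52, 1.55 | 1.50, 1.50, 1.49 |
| Equal intervals, ILD stops 80% of DOAC and 40% of VKA users (*g* = 28, 56, 84) | 1.03, 0.80, 0.70 | 1.44, 1.42, 1.32 |
| DOAC 84 days, VKA 28 days, ILD always stops the drug | 0.53 | 1.24 |

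**The case against.** Several stronger readings are tempting, and the protocol does not support them.

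- **That these events are lost to the study.** The 30/90-day rule is written for the on-treatment analysis only. ITT does not censor at discontinuation and keeps the events. This lowers the stakes but does not remove them. ITT also counts all time after stopping, so it answers a different question, and the protocol does not rank it above the on-treatment analysis.
- **That refillers' days 31 to 90 are event-free by construction.** They are not. ILD in that time counts when a prescription follows. The fault is selection on a later prescription.
- **That the hazard ratio is known to be biased, or biased towards hiding a signal.** The direction depends on quantities the protocol does not give. The 1.47 and 0.68 figures need a threefold difference in refill interval and *p* = 0.5; at *p* = 0.1 the first falls to 1.07.
- **That patients who stop never leave on-treatment follow-up, because the exit list in section 5.4 names switching but not stopping.** Section 5.5 covers stopping.
- **That ending follow-up at a switch, with no tail, is an error.** It avoids crediting one drug's events to the other and is a defensible choice.

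The strongest remaining objection concerns *p*. Section 5.5 refers to anticoagulant prescriptions in general. Read literally, a patient moved to another anticoagulant within 90 days has no qualifying gap, and ILD recorded before that move still counts. Loss is then confined to patients who receive no anticoagulant at all in that time. All patients have AF or VTE, so this group may be small, and nothing in the protocol supports a high *p*. The objection limits the size of the problem. It does not justify a rule that looks ahead.

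**Conclusion.** The point holds for the on-treatment analysis. Section 5.5 itself fixes the 30-day tail, the 90-day bridge and the backdated censoring, so the asymmetry is not a detail left for later. ILD recorded more than 30 days after the last prescription is lost when no further anticoagulant follows within 90 days. ILD recorded within 30 days is unaffected.

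Confidence is high for the asymmetry and for the selective loss of events. It is only conditional for bias in the hazard ratio: close to none if refill intervals and stopping after ILD are equal in both arms, and possible in either direction if they differ. Every percentage and ratio above rests on assumed intervals, stopping probabilities and delays. As no planned analysis varies the window, the study as written could not show how much the result depends on it. The rule should be changed before exposure episodes are programmed.

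**What to change.** Define on-treatment time in section 5.5 with one forward-looking allowance that serves both within and at the end of an episode. After each prescription the patient stays exposed for a set time and exits on the first day beyond it without a new prescription. The set time would be prescription length plus a fixed grace period, or the plan's own 90 days where length is not recorded. Keep censoring at a switch, including between DOAC and VKA. A tail after switching would count up to 90 days on one arm's drug as the other's. Report the rule as written, with its 30-day tail, as a sensitivity analysis in section 5.6.6.

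With a 90-day allowance and no diagnostic delay, all drug-stopping ILD is counted at any refill interval up to 90 days. The cost is a short rewording of section 5.5, one line in section 5.6.6 and reprogramming of exposure episodes. There are two drawbacks. Some unexposed days after true stopping are counted as exposed, and some loss remains when diagnosis is delayed, as the 90-day columns above show.
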